3.3.5. PRIOR AND CONCOMITANT THERAPY

Prior and concomitant medication are documented throughout the study.

During the 104-week treatment and assessment period of the study, subjects are not allowed to initiate DMARDs (other than MTX for subjects who completed the preceding Study ALX0061-C201, see below).

Permitted Medication

Subjects who completed the prior combination therapy study (Study ALX0061-C201) will receive ALX-0061 and will be recommended to continue

with MTX, while subjects who completed the prior monotherapy study (Study ALX0061-C202; except those who were assigned to TCZ) will receive ALX-0061 as monotherapy.

MTX will not be considered one of the study agents and the MTX dose can be adjusted at the Investigator's discretion.

Commercially available MTX will be used in this study and will not be provided by the Sponsor. Continued supplementation with oral folic acid or oral folinic acid should be given at the discretion of the treating physician for patients on MTX.

Subjects treated with NSAIDs (including aspirin and selective cyclooxygenase 2 inhibitors) and other analgesics (except high-potency opioid analgesics; see prohibited medication) should receive the usual marketed doses approved in the country in which the study is being conducted, and should be on a stable dose whenever possible until the Week 104 visit, or until the Early Termination Visit. Changes in the dose may be done at the discretion of the Investigator if he/she feels it is medically justified. Whenever possible, short-acting NSAIDs and other analgesics should not be administered within 6 hours before study assessments. Long-acting ones can be maintained at their usual dosing intervals before study assessments.

Subjects treated with oral corticosteroids should receive a stable dose equivalent to ≤ 10 mg of prednisone/day, up to and including Week 104, or until the Early Termination Visit. The dose of oral corticosteroid may be changed at the discretion of the Investigator.

The number of intra-articular (i.a.) corticosteroid injections is limited to 2 injections over a 104-week period. The joint(s) affected by the procedure(s) will be considered as swollen and tender for 28 days/4 weeks in the data analyses from the date of the procedure onward.

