#### **4.2.2 *Presentation of treatment groups***

The following treatment group labels will be used in the tables, listings and figures, unless specified otherwise:

- ALX-0061 150 mg q2w + MTX (C201 PBO + MTX)
- ALX-0061 150 mg q2w + MTX (C201 75 mg q4w + MTX)
- ALX-0061 150 mg q2w + MTX (C201 150 mg q4w + MTX)
- ALX-0061 150 mg q2w + MTX (C201 150 mg q2w + MTX)
- ALX-0061 150 mg q2w + MTX (C201 225 mg q2w + MTX)
- ALX-0061 150 mg q2w + MTX (C201 all subjects)
- ALX-0061 150 mg q2w (C202 150 mg q4w)
- ALX-0061 150 mg q2w (C202 150 mg q2w)
- ALX-0061 150 mg q2w (C202 225 mg q2w)
- ALX-0061 150 mg q2w (C202 all subjects)
- All subjects

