## 6 EFFICACY

### 6.1 Main Efficacy Analysis

No inferential statistical analyses will be performed. All tables will be presented by treatment group and overall, including treatment groups defined by previous dosing regimen of the parent trial (cfr. section 4.2.2). All analyses will be run on the ITO. The main analysis will be on observed cases (OC).

Continuous efficacy endpoints will be summarized as follows:

- Actual values: descriptive statistics (mean, 95% CI on the mean [normal approximation], SE, median, minimum, and maximum) per endpoint and time point. The baseline value from the parent trial will be included to the summary, if applicable.
- Changes from baseline: baseline adjusted LS means and 95% CI from an ANCOVA model with treatment as factor and baseline as covariate, median, minimum and maximum per endpoint and post-baseline time point.

This will be done for the following parameters: ACR-N, DAS28(CRP), DAS28(ESR), SDAI, CDAI, HAQ-DI, SF-36 physical and mental component scores, FACIT-Fatigue, duration of morning stiffness, patient's assessment of pain (VAS-scale), patient's global assessment of disease activity (VAS-scale), physician's global assessment of disease activity (VAS-scale), CRP, ESR, TJC68, TJC28, SJC68, SJC28, MTX dose, corticosteroids dose. Different types of systemic corticosteroids will be converted to Prednisolone equivalent doses before calculating the cumulative dose of corticosteroids. The cumulative dose will be given in mg/day (Please refer to Appendix 2 section 16.2 for more details).

Categorical efficacy endpoints will be presented using a frequency tabulation of the parameter at each time point, including a Wilson score 95% CI on the percentage of subjects in the category of interest. The baseline value from the parent trial will be included to the summary, if applicable. This will be done for the following parameters: ACR20, ACR50, ACR70, EULAR response (including EULAR good response), DAS28(ESR) low disease activity / remission / maintained remission / maintained low disease activity, DAS28(CRP) low disease activity / DAS(CRP) < 2.6 / maintained DAS(CRP) < 2.6 / maintained low disease activity, SDAI low disease activity / remission / maintained remission, CDAI low disease activity / remission / maintained remission, Boolean remission / maintained remission, HAQ-DI clinically meaningful improvement, HAQ-DI normal physical function, MTX dose reduction rate, MTX discontinuation rate.

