- Disease activity is defined as follows based on the actual value of DAS28(ESR):
  - Remission:  $DAS28(ESR) < 2.6$
  - Low disease activity:  $2.6 \leq DAS28(ESR) \leq 3.2$
  - Moderate disease activity:  $3.2 < DAS28(ESR) \leq 5.1$
  - High disease activity:  $DAS28(ESR) > 5.1$
  - Pooled category Remission + Low disease activity will be shown as well
- Disease activity is defined as follows based on the actual value of DAS28(CRP):
  - $DAS28(CRP) < 2.6$
  - Low disease activity:  $2.6 \leq DAS28(CRP) \leq 3.2$
  - Moderate disease activity:  $3.2 < DAS28(CRP) \leq 5.1$
  - High disease activity:  $DAS28(CRP) > 5.1$
  - Pooled category  $DAS28(CRP) < 2.6$  + Low disease activity will be shown as well
- Boolean remission is defined as follows:
  - Yes:  $TJC28 \leq 1 \text{ AND } SJC28 \leq 1 \text{ AND } VASPA \leq 1 \text{ cm AND } CRP \leq 1 \text{ mg/dL}$
  - No: else
- Clinically meaningful improvement in HAQ-DI (clinically meaningful improvement from baseline – absolute change) is defined as follows:
  - Yes:  $\Delta HAQDI \geq 0.25$
  - No:  $\Delta HAQDI < 0.25$

- Normal physical function based on HAQ-DI is defined as follows:
  - Yes:  $HAQDI \leq 0.5$
  - No:  $HAQDI > 0.5$
- CDAI score = TJC28 + SJC28 + VASPA (cm) + VASPHA (cm)
- CDAI classification:
  - Remission:  $CDAI \leq 2.8$
  - Low disease activity:  $2.8 < CDAI \leq 10$
  - Moderate disease activity:  $10 < CDAI \leq 22$
  - High disease activity:  $22 < CDAI$
  - Pooled category Remission+Low disease activity will be shown as well
- SDAI score = TJC28 + SJC28 + VASPA (cm) + VASPHA (cm) + CRP (mg/dL)
- SDAI classification:
  - Remission:  $SDAI \leq 3.3$
  - Low disease activity:  $3.3 < SDAI \leq 11$
  - Moderate disease activity:  $11 < SDAI \leq 26$
  - High disease activity:  $26 < SDAI$
  - Pooled category Remission+Low disease activity will be shown as well
- Maintained remission at Week x: remission at Week x and all consecutive time points.

MTX and corticosteroid dose related endpoints will be derived as follows:

- MTX dose decrease from baseline at W0, W48 and W104:
  - Yes: daily dose at Week 0/ Week 48 / Week 104 visit < baseline dose
  - No: else
- Discontinuation of MTX dose at W0, W48 and W104:
  - Yes: daily dose at Week 0/ Week 48 / Week 104 visit = 0
  - No: else
- Change from baseline of MTX dose at Week 0/ Week 48 / Week 104
- Change from baseline of corticosteroid dose at Week 0/ Week 48 / Week 104

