**Table 14.2.1.13.3: RA therapy reduction – Actual values and change from baseline in MTX dose**

Descriptive statistics of the actual values and change from baseline in MTX dose at 1 and 2 years. Additionally, the change from baseline at each time point will be modelled using an ANCOVA model with treatment group and baseline MTX dose as covariates and the LS means with 95% CI will be reported.

Population: ITO.

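### The ANCOVA for change in MTX dose is not limited to C201; if C202 monotherapy subjects enter with dose 0, its LS means show an MTX reduction in C202 and understate the one in C201

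*SAP*

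**What the plan says.** SAP 6.1 sets one rule for changes from baseline in all listed continuous parameters, MTX dose among them: "baseline adjusted LS means and 95% CI from an ANCOVA model with treatment as factor and baseline as covariate". It adds that "All analyses will be run on the ITO". The entry for Table 14.2.1.13.3 applies this to MTX dose at 1 and 2 years, "modelled using an ANCOVA model with treatment group and baseline MTX dose as covariates", again with ITO as the population.

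The default groups in SAP 4.2.2 are five C201 arms, three C202 arms (for example "ALX-0061 150 mg q2w (C202 150 mg q4w"), pooled columns for each study and a grand total. Protocol 3.3.5 says that subjects from the monotherapy study, "except those who were assigned to TCZ) will receive ALX-0061 as monotherapy". Its prohibited-medication list bars DMARDs and exempts MTX only for those who came from C201, whose MTX dose the investigator may adjust.

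SAP 12.3 flags MTX discontinuation as "Yes: daily dose at Week 0/ Week 48 / Week 104 visit = 0". It states no C201 restriction and gives no value for a subject who was never on MTX. Elsewhere the SAP does make the distinction: Listing 16.2.7.1 reports the relation of adverse events to MTX for C201 subjects only.

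**The concern.** Change in MTX dose has meaning only for subjects who take MTX. A single ANCOVA across both studies adjusts every arm to a common baseline dose. If the C202 arms sit at baseline 0 and change 0, that common dose lies well below what C201 subjects take and above what any C202 subject takes. The adjusted means for C202 are then extrapolations from a point mass at zero, and those for C201 describe a baseline dose that is not theirs. The table is meant to show how far C201 subjects reduce MTX over two years, so the adjusted figures at stake are the ones a reader would look for.

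**Working it through.** The documents give no MTX figure, effect size or split by parent study, so there is no stated value to reproduce. The check is algebra, supported by simulation.

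**Inputs from the documents.** Eight arms (five C201, three C202); model with arm and baseline MTX dose; ITO population; two-sided 95% intervals; at most about 501 subjects.

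**Assumptions.** C202 dose coded 0. LS means evaluated at the pooled mean baseline (the SAP names no covariate value). C201 share s between 0.50 and 0.75. C201 mean baseline dose mu = 15 units, with coefficient of variation (CV) 0.15 to 0.40. A fraction d of C201 subjects, from 5 to 20%, stop MTX irrespective of dose, and the rest are unchanged.

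**LS means.** For arm j, LS mean = mean change + b × (pooled mean baseline − arm mean baseline). C202 baselines do not vary, so the slope b comes from C201 alone. The pooled mean baseline is s × mu. Therefore:

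- C202 arm: 0 + b × (s·mu − 0) = b·s·mu, where the true change is 0.
- C201 arm: mean change + b × (s·mu − mu) = mean change − b·(1−s)·mu.

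Both are correct only if b = 0. If a fraction d stop, the expected change at baseline x is −d·x, so b = −d and the C201 mean change is −d·mu. Both LS means then equal −d·s·mu, and the C201 reduction is understated by the proportion 1−s.

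**Numbers.** Take s = 0.60 (60 per C201 arm and 67 per C202 arm: 300 of 501), mu = 15 and d = 10%. The pooled mean baseline is 0.60 × 15 = 9.0.

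- C202: −0.10 × 9.0 = −0.90, true 0.
- C201: −1.50 + 0.10 × 0.40 × 15 = −0.90, true −1.50; understatement 0.60/1.50 = 40%.

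Simulation at CV 0.27:

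| d | C201-arm LS mean (true) | C202-arm LS mean (true) |
|---|---|---|
| 5% | −0.48 (−0.75) | −0.42 (0) |
| 10% | −0.88 (−1.50) | −0.90 (0) |
| 20% | −1.79 (−3.00) | −1.81 (0) |

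Over s = 0.75 to 0.50, the understatement 1−s is 25 to 50%.

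**Standard errors.** C202 subjects add degrees of freedom but no residual variation, so the residual SD falls to about sqrt(s) of its C201 value: 0.71 to 0.87 over the range, and 0.775 at s = 0.60. In the 10% case the model SE of a C201-arm LS mean is 0.562 against an empirical 0.642. Across the simulated settings, the interval covers its own target in about 86 to 94% of trials and the true C201-arm change in 60 to 85%; the second range reflects the shift as well as the small SE.

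**Interval width.** Relative to a C201-only model, the ratio for a C201 arm is sqrt(s × (1 + (1−s)²/(5·CV²))). Over the range of s it is 0.81 to 0.95 for CV 0.25 to 0.40, 0.99 to 1.06 at CV 0.20, and 1.08 to 1.27 at CV 0.15. For C201 pooled, the factor 5 drops out and the ratio is 1.02 to 2.46.

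**C201-only model, 10% case.** LS mean −1.49 (true −1.50), model SE 0.600 against empirical 0.606, coverage about 96%.

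**The case against.** The strongest objection is that zero coding is inferred. The only dose-equals-zero rule defines a discontinuation flag, which naturally concerns people who had a dose. A monotherapy subject would normally have no MTX record, and SAP 4.2.1 includes in changes from baseline only subjects with both values. If the C202 dose is missing, those rows drop out and the problem does not arise. It stands that the SAP does not settle this. But zero is the natural reading: SAP 12.3 requires the discontinuation flag at Week 0, while SAP 5.6 says that therapies stopped before the study are not recorded, so an absent record has to be read as 0. Nothing exempts C202 from that derivation.

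The second objection is that an LS mean at a common baseline is a different quantity from the raw arm mean, and that the table is descriptive. Both are true. Yet the common baseline here belongs to neither study, and the intervals fall short of 95% even for their own target. The table entry does provide descriptive statistics of change alongside the LS means, although SAP 6.1 lists only the median, minimum and maximum beside them for changes. SAP 6.1 rules out inferential analyses, MTX dose is absent from the endpoint list in SAP 3.3, and the column labels carry MTX only for C201. These points limit the harm; they do not make the adjusted values right.

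Two stronger readings are tempting. A reader might infer that the intervals are simply too narrow. They are not in general: evaluation far from the C201 mean adds a leverage term, so arm intervals can be wider than C201-only ones, and the pooled C201 intervals are wider throughout the range examined. A reader might also fix the C201 mean change at −1.5 and steepen the slope to −0.3, which turns the LS mean positive: −1.5 + 0.3 × 0.375 × 15 = +0.19 with s = 5/8. That requires subjects below a dose of 10 to increase MTX, since −1.5 − 0.3 × (10 − 15) = 0. The documents give no ground for that pattern.

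**Conclusion.** The point holds with conditions. As written, the MTX-dose ANCOVA takes in three arms that may not use MTX, and the SAP leaves their dose coding open. If the dose is 0, LS means are taken at the pooled mean baseline and b is not 0, then C202 arms show a change that did not happen and C201 arms are shifted by −b·(1−s)·mu. When the slope arises from subjects stopping MTX, the two studies look alike and the C201 reduction is understated by 25 to 50% over the assumed shares. C201-arm standard errors are too small for their own sampling error, and the intervals miss the true C201 change more often than stated. The share, mean dose, spread and stopping rate are all assumptions. A reader might conclude that the SAP prescribes zero for C202, or that the whole table is unusable; it says nothing on the first, and the unadjusted statistics are untouched on the second. This is a limited defect in a descriptive table, worth correcting because the correction is so cheap.

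**What to change.** In SAP 6.1 and in the entry for Table 14.2.1.13.3, state that the MTX-dose summaries and ANCOVA include C201 subjects only, with LS means evaluated at the C201 mean baseline dose. Show *not applicable* in the C202 columns and label the total *C201 all subjects*. The cost is one sentence in each place and one filter in the program. No information is lost, because C202 carries none on MTX dose, and the open question of zero or missing no longer affects this table.

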## 6.2 Other Efficacy Analyses

The sensitivity of results to missing data will be assessed by conducting a sensitivity analysis using LOCF imputed cases. Missing post-baseline values are imputed by the last non-missing preceding post-baseline value. Baseline itself is not imputed.

The sensitivity analysis will be done for the following efficacy endpoints:

- ACR20/50/70
- DAS28(ESR) actual values and changes from baseline
- DAS28(ESR) remission/low disease activity
- DAS28(CRP) actual values and changes from baseline
- DAS28(CRP) < 2.6/low disease activity

A second sensitivity analysis will be done using NRI imputed cases. Missing post-baseline ACR values are imputed with the value corresponding to that of non-responders.

This sensitivity analysis will be done for the following efficacy endpoints:

- ACR20/50/70
- DAS28(ESR) remission/low disease activity
- DAS28(CRP) < 2.6/low disease activity

In addition, for the same efficacy endpoints, a subgroup analysis will be conducted on the observed cases.

The following subgroups will be considered:

- Age category (<65 yrs at baseline, >= 65 yrs at baseline)
- Geographic region
- If any subcategory has less than 10% of the total number of patients then the subgroup analysis will not be produced.

A detailed list of tables can be found in section 13.2.

## 7 SAFETY

### 7.1 Adverse Events

All safety summaries will be based on the safety population and presented by treatment group (see section 4.2.2). As study drug treatment is not interrupted between the parent study and this study, all adverse events reported in this study are considered treatment-emergent. However, unless specified otherwise, only adverse events that started after the first dose of C203 will be considered in the tables.

All adverse events will be coded and classified by System Organ Class (SOC) and Preferred Term (PT) using the medical dictionary for regulatory activity (MedDRA) that is current at the time of database lock.

A TEAE will be categorized as study drug-related if the relationship to study drug is reported to be 'possibly related' or 'related', or missing. In tabulations this categorization

will be used, but in the listings the original reported relationship will be presented. If the relationship is reported to be 'not applicable', it will not be considered in the tabulations.

A TEAE is reported as related to study procedure or not related to study procedure. Missing study procedure relationship will be considered as related.

A general summary table with AE events starting after first dose of C203 only will be produced to report the number and percentage of subjects with at least one event, the number of events and the incidence per 100 patient years, which will be calculated as:  $100 \times (\text{Number of subjects with AE}) / (\text{Total number of years observed while on C203, summed for all subjects})$ . Percentages will be calculated out of the number of subjects in the relevant treatment group.

The following categories will be included in the summary table:

- TEAE
- serious TEAE
- TEAE leading to death
- severe TEAE as classified by the investigator
- TEAE for which the study drug was interrupted
- TEAE for which the study drug was discontinued
- study drug-related TEAE
- serious study drug-related TEAE
- injection-site reaction.

Note that the TEAE here refers to the AEs starting after first dose of study drug in C203 study.

A similar summary table will be produced for all TEAEs including those of the parent trials (C201 and C202). Any event happening either on parent trial or on the current trial will be considered for deriving the number and percentage of subjects with at least one event, and the number of events. The incidence per 100 patient years will be calculated as:  $100 \times (\text{Number of subjects with AE}) / (\text{Total number of years observed starting from the first dose in parent trial, summed for all subjects})$ .

Another summary table will be presented selecting adverse events of special interest. Search criteria for these adverse events can be found in section 16.5.

The following categories will be included in the summary table:

- infection
- serious infection (requiring hospitalization or i.v. antimicrobial treatment)
- opportunistic infection, excluding TB
- active TB infection
- latent TB infection
- Herpes zoster infection
- malignancy
- hypersensitivity reaction (including anaphylaxis and angioedema)
- hypersensitivity reaction (including anaphylaxis and angioedema) leading to withdrawal
- GI perforation
- demyelinating disorder
- MACE

This table will represent events which occurs only after the first dose of study drug in C203 study.

One more summary table for AEs of special interest will be produced including events from the parent trials as well. Any event happening either on parent trial or on the current trial will be considered for deriving the number and percentage of subjects with at least one event, and the number of events. The incidence per 100 patient years will be calculated as:  $100 \times (\text{Number of AEs}) / (\text{Total number of years observed starting from the first dose in parent trial, summed for all subjects})$ .

Tables by SOC and PT will report the number and percentage of subjects with at least one event, occurring only after the first dose of study drug on C203 study. Percentages will be calculated out of the number of subjects in the relevant treatment group.

These tables will be prepared for the following selections of AEs:

- TEAEs
- TEAEs by severity (Mild, Moderate, Severe)
- TEAEs with an incidence of at least 3%
- serious TEAEs
- non-serious TEAEs
- study drug-related TEAEs
- study procedure-related TEAEs
- TEAE for which the study or the study drug were discontinued

The tables by SOC and PT will be sorted in descending order starting from the SOC with the highest incidence in the all subjects group. If the total incidence for any two or more SOCs is equal, the SOCs will be presented in alphabetical order. Within each SOC, the PTs will be presented in the same manner as the SOCs. At each level of subject summarization, a subject is counted once if the subject reported one or more events. In the summary table by severity, if a subject reported multiple occurrences of the same TEAE, only the most severe will be presented. TEAEs with missing severity will be presented in a separate 'Missing' category.

The AE onset day and the AE duration will not be presented in the tabulations, but will be listed. Their derivation is provided in section 12.4.1.

A detailed list of tables and listings can be found in section 13.4 and section 15.4, respectively.

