3.1. OVERALL STUDY DESIGN

3.1.1. STUDY OVERVIEW

This is a multicenter, open-label extension (OLE) Phase II study of ALX-0061 administered s.c. in subjects with active RA who have completed the treatment and assessment period of one of the preceding Phase IIb studies with ALX-0061 (ALX0061-C201 and ALX0061-C202; placebo and ALX-0061 treatment arms only) and who achieved at least 20% improvement in swollen joint count (SJC) and/or tender joint count (TJC) (66/68 counts) at the final visit of the preceding study.

An overview of the study design is included in [Figure 1](#).

Figure 1: Overview of the design of Study ALX0061-C203

^a Placebo and ALX-0061 treatment arms only

^b Stopping criteria beginning at Week 12 and every 12 weeks of OLE for non-responders: patients with < 20% improvement in both TJC and SJC from baseline (of the respective initial Phase IIb study) will have study drug injections discontinued, and will be discontinued from the study in order to receive standard of care. q2w: every 2 weeks.

Eligible subjects will receive ALX-0061 150 mg s.c. injections, beginning at Week 0 of the OLE and every 2 weeks (q2w) thereafter up to and including Week 102. Eligible subjects from Study ALX0061-C201 will also continue their MTX treatment.

The dose regimen, 150 mg s.c. every two weeks (q2w), was selected as this dose level is expected to be effective based on exposure-response modelling (PK-DAS28) of ALX-0061 using data from studies ALX-0061-1.1/10 and ALX0061-C102. Moreover, this regimen is covered by adequate safety margins, when comparing the model predicted human exposure with the observed exposure in the toxicity studies.

In the current OLE study, maintenance of the response will be reassessed at the study visits at Weeks 12, 24, 36, 48, 60, 72, 84 and 96. Subjects who fail to maintain response and meet Efficacy Discontinuation Criteria (< 20% improvement

in both SJC and TJC compared to baseline of preceding study) will be discontinued from the OLE study.

Evidence for efficacy will be obtained by analysis of the ACR20, ACR50, ACR70, ACR-N response rates, EULAR response, and measures of remission using the DAS28, the CDAI, the Simplified Disease Activity Index (SDAI), and the Boolean remission definition. Other RA domains, such as improvement in physical function and health-related quality-of-life, will be evaluated using the HAQ-DI, FACIT-fatigue scale, and the SF-36 questionnaires.

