3.2.1. INCLUSION CRITERIA

Each potential subject must satisfy all of the following criteria to be enrolled in the study:

1. Must have been eligible for one of the preceding Phase IIb studies with ALX-0061 (ALX0061-C201 or ALX0061-C202), have been randomized to placebo or one of the ALX-0061 arms (subjects randomized to tocilizumab [TCZ] in Study ALX0061-C202 are not eligible) and completed the entire treatment and assessment period of the preceding studies (i.e., 24 weeks for Study ALX0061-C201 and 12 weeks for Study ALX0061-C202).
2. Must have reached at least 20% improvement in SJC and/or TJC at Week 24 for subjects participating in the preceding Phase IIb ALX0061-C201 study, or at Week 12 for subjects participating in the preceding Phase IIb ALX0061-C202 study.
3. Female subjects of childbearing potential (excluding postmenopausal women, sterilized, ovariectomized, and hysterectomized women) must agree to use 2 generally accepted adequate contraceptive methods of which 1 is a barrier method (e.g., hormonal contraception stabilized for at least 1 month [oral, patch, depot, injectable, vaginal ring] in combination with condom by partner) or should agree upon continuous abstinence from heterosexual contact from screening/baseline until at least 6 months after last dosing.
Male subjects must use condoms for the duration of the study and for at least 6 months after last administration of study drug.
4. Ability to comprehend and willingness to sign the informed consent form (ICF).
5. An understanding of and ability and willingness to adhere to the study visit schedule and other protocol requirements.

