3.3.1. IDENTITY OF STUDY DRUG

- Study drug:
 - Active substance: ALX-0061 Nanobody.
 - Activity: ALX-0061 Nanobody binds to the IL-6R and inhibits the interaction between the IL-6 ligand and the receptor subunit, thereby preventing receptor signaling.
 - Pharmaceutical formulation: ALX-0061 Drug Product is a clear, yellow to brown-yellow solution in an aqueous medium with a nominal concentration of 150 mg/mL of ALX-0061 and containing the following excipients: L-histidine, L-histidine hydrochloride monohydrate, polysorbate 80 (Tween 80), sucrose, and water for injections. ALX-0061 will be supplied as a sterile liquid for s.c. injection at a volume of 1.0 mL in pre-filled single-use syringes. No preservatives are present.
 - Route and volume of administration: s.c. injections at a volume of 1.0 mL.

The Sponsor will be providing adequate supplies of ALX-0061 for this study.

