3.5. ADVERSE EVENT EVALUATION AND REPORTING

3.5.1. ADVERSE EVENTS

AE definitions will be followed as stated in the "Note for Guidance on clinical safety data management: definitions and standards for expedited reporting" (International Conference on Harmonization [ICH] topic E2A).

An AE is any untoward medical occurrence in a clinical study subject administered a medicinal (investigational or non-investigational) product. An AE does not necessarily have a causal relationship with the treatment. An AE can therefore be any unfavorable and unintended sign (including an abnormal finding), symptom, or disease temporally associated with the use of a medicinal (investigational or non-investigational) product, whether or not considered related to that medicinal (investigational or non-investigational) product.

This includes any occurrence that is new in onset or aggravated in severity or frequency from the baseline condition, or abnormal results of diagnostic procedures, including laboratory test abnormalities.

In differentiating between medical history and AEs, the following points will be considered:

- Conditions that started before signing of informed consent and for which no symptoms or treatment are present up to the timing of signing of informed consent are recorded as medical history (e.g., seasonal allergy without acute complaints).
- Conditions that started before signing of informed consent and for which symptoms or treatment are present after signing of informed consent, but with unchanged severity, are recorded as medical history (e.g., allergic pollinosis).
- Conditions that started or deteriorated after signing of informed consent will be documented as AEs.

All AEs will be reported from the time a signed and dated ICF is obtained until completion of the subject's last visit.

A TEAE is any AE temporally associated with the use of study drug, whether considered related to the study drug or not. TEAEs are recorded from the start of study drug administration, until completion of the subject's last visit.

It is the responsibility of the Investigator to collect all AEs (both serious and non-serious) derived by spontaneous, unsolicited reports of subjects, by

observation, and by routine open questioning (e.g., "How have you felt since I saw you last?"; "Is there anything new that you wish to discuss?").

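### The two adverse event summaries that add the parent trials count former C201 placebo subjects' placebo-period events and person-time as treatment-emergent experience

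*SAP*

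**What the plan says.** By default, the tables in SAP 7.1 count events with onset after the first C203 dose. Two further summaries add the parent trials: Table 14.3.1.2 for all TEAEs and Table 14.3.1.4 for adverse events of special interest (AESIs). For both, the numerator rule is "Any event happening either on parent trial or on the current trial will be considered" and the denominator is "Total number of years observed starting from the first dose in parent trial, summed for all subjects". The rate counts subjects with an event in the first table and events in the second.

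The same section opens with the statement "As study drug treatment is not interrupted between the parent study and this study", and concludes from it that every event reported in C203 is treatment-emergent.

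The following passages show who falls under these rules:

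- Protocol 3.2.1 admits subjects who "have been randomized to placebo or one of the ALX-0061 arms".
- SAP 4.2.2 gives the former C201 placebo subjects their own column ("ALX-0061 150 mg q2w + MTX (C201 PBO + MTX") and pools them into the C201 all-subjects and All subjects columns. It lists no C202 placebo group.
- Protocol 3.1.1 states "Eligible subjects will receive ALX-0061 150 mg s.c. injections, beginning at Week 0 of the OLE".
- Protocol 3.3.1 identifies the study drug: "Active substance: ALX-0061 Nanobody".
- Protocol 3.5.1 states "TEAEs are recorded from the start of study drug administration, until completion of the subject's last visit".

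I found no rule in SAP 7.1, the table descriptions in SAP 13.4 or the list of changes in SAP 11 that removes, splits off or footnotes the placebo period in these two tables.

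**The concern.** A subject randomized to placebo in C201 first meets ALX-0061 at C203 Week 0. By the protocol's own definition, an event during the C201 placebo period is not treatment-emergent for ALX-0061. The parent-inclusive rule nevertheless starts the clock at the first parent-trial dose for everyone, so it brings placebo events and placebo time under column headings that name ALX-0061.

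These are the only two of the twelve planned adverse event tables that give incidence over the combined parent and extension period, so a reader interested in long-term risk may well turn to them. The AESI table includes serious infection, malignancy, GI perforation and MACE, where one or two events can decide how a row is read. A subject whose only such event occurred on placebo would be counted in the ALX-0061 total.

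**Working it through.** **Inputs**

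- The parent period is 24 weeks in C201 and 12 weeks in C202 (Protocol 3.2.1). I assume that C201 placebo subjects stayed on placebo for all 24 weeks. The C201 protocol is not among the documents.
- The last C203 dose is at Week 102 and the Follow-up Visit is 12 weeks later (Protocol 3.1.1). 102 + 12 = 114 weeks, which reproduces the stated maximum duration.
- Early leavers who keep their consent also return 12 weeks after their last dose (Protocol 3.4.1.3). A last dose at Week 50 gives 50 + 12 = 62 weeks, and at Week 24 gives 24 + 12 = 36 weeks.
- SAP 7.1 does not say when observed time ends. I take the Follow-up Visit.
- The documents give neither the number of former placebo subjects nor any event rate for the two treatments. Let *r* be the ratio of the placebo event rate to the ALX-0061 event rate, and vary it from 0.5 to 2.

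**Step 1: placebo share and event-rate factor in the former placebo column**

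With *c* weeks of C203 follow-up, the placebo share is 24/(24 + *c*). The reported event rate divided by the ALX-0061-only event rate is (24*r* + *c*)/(24 + *c*). This applies to Table 14.3.1.4, which counts events.

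| Case | *c* (weeks) | Placebo share | Factor, *r* = 0.5 | Factor, *r* = 2 |
|---|---|---|---|---|
| Full follow-up | 114 | 24/138 = 17% | 126/138 = 0.91 | 162/138 = 1.17 |
| Last dose Week 50 | 62 | 24/86 = 28% | 74/86 = 0.86 | 110/86 = 1.28 |
| Last dose Week 24 | 36 | 24/60 = 40% | 48/60 = 0.80 | 84/60 = 1.40 |

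If observed time ended at Week 104 instead, the completer's share would be 24/128 = 19%.

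**Step 2: the subject-count table**

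Table 14.3.1.2 divides subjects with an event by total years. Under a constant hazard λ per year and *T* years of observation this is 100(1 − e^(−λ*T*))/*T*, which falls as *T* grows even when *r* = 1. With λ = 0.5 it is 30.42 for *T* = 114 × 7/365.25 = 2.185 years and 27.73 for *T* = 138 × 7/365.25 = 2.645 years. With λ = 0.05 the values are 4.74 and 4.68. The factors in Step 1 are therefore only approximate for this table.

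**Step 3: pooled columns**

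Assume equal numbers in the five C201 and three C202 groups of SAP 4.2.2, full follow-up, and one common ALX-0061 event rate. With placebo share *f*, the rate factor is 1 + *f*(*r* − 1).

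- C201 all subjects: *f* = 24/(5 × 138) = 3.5%. The factor is 0.983 (*r* = 0.5) or 1.035 (*r* = 2).
- All subjects: *f* = 24/(5 × 138 + 3 × 126) = 24/1068 = 2.2%. The factor is 0.989 or 1.022.
- If former placebo subjects make up 5% to 20% of everyone, with the rest split 4:3 between C201 and C202, *f* for All subjects runs from 0.9% to 3.6%.

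**The case against.** The case for leaving the tables alone has four parts.

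1. *The sentence on uninterrupted treatment may be harmless.* Protocol 3.4.1.1 uses the term study drug for parent-trial injections without separating arms, so the sentence can be read as describing an unbroken injection schedule. It also supports only the labelling of events reported in C203, and deleting it would leave both tables unchanged. This stands. A reader might infer that the sentence causes the problem, but the numerator and denominator rules do.
2. *The ALX-0061-only figures are already planned.* Tables 14.3.1.1 and 14.3.1.3 give the same summaries for events after the first C203 dose. This stands for the former placebo column, but those tables cannot replace the pooled combined-period columns, because they also drop the valid parent-trial ALX-0061 experience of the other arms.
3. *The origin is disclosed.* Both table titles say that parent-trial events are included, and the column label names placebo. This stands in part. A reader could difference event counts against the C203-only tables, but not subject counts, since a subject may have events in both periods. The pooled columns carry no flag.
4. *The pooled effect is small.* This stands for common events, at about 1 to 3.5%. It does not help with an AESI row that contains only a few events.

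A reader might also infer that the placebo time dilutes the ALX-0061 rates. That needs a lower event rate on placebo, and the documents give no rates. Nor do they support calling these tables the study's main safety output: SAP 3.3 notes that the protocol ranks no endpoints, and the SAP's default is C203-onset events.

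**Conclusion.** The point holds for two tables and three columns. In Tables 14.3.1.2 and 14.3.1.4 the former C201 placebo column mixes placebo and ALX-0061 experience, and the mixture passes unflagged into the C201 all-subjects and All subjects columns. The C203-only tables are correct. So are the columns for subjects who were on ALX-0061 in the parent trial, and the C202 columns.

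The effect can be material in the former placebo column, where placebo time is 17% to 40% of person-time in the cases shown. It is small in the pooled rates, although a single rare AESI could still be misattributed. The bias could go either way. The figures rest on a full 24 weeks of placebo, observation to the Follow-up Visit, and, for the pooled columns, equal arms with full follow-up and a common ALX-0061 rate. The change is worth making because the rates would then describe ALX-0061 exposure, as the column labels imply.

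**What to change.** 1. In Tables 14.3.1.2 and 14.3.1.4, start both events and person-years for former C201 placebo subjects at their first ALX-0061 dose (C203 Week 0), in their own column and in both pooled columns.
2. Show the C201 placebo period of these subjects in a separate column, labelled as placebo and kept out of the pooled totals.
3. Reword the opening statement of SAP 7.1 so that it excepts subjects who received placebo in C201.

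The cost is a start-date rule for one group, one added column and a few words in the SAP; no new data are needed. There is a small downside: the former placebo group's ALX-0061 column will repeat its counterpart in the C203-only tables. The separate placebo column keeps that group's parent-trial data in tables whose titles promise them.
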